**1.2. Patient Enrollment and Group Formation**

The inclusion criteria were as follows: (1) parents agreed to participate in the study (2) infants born in our hospital, who were followed up in the NICU, with a gestational age of <34 weeks and a birth weight of 1000-2000 grams. Infants who indicated UVC placement, and for whom NIRS measurements were taken both before and after UVC placement were included in the UVC (+) Study Group. Infants who did not have a UVC but matched the Study Group regarding gestational age and birth weight constituted the UVC (-) Control Group.

Infants who died during the first week of life, were transferred to another hospital, had chromosomal anomalies, major congenital anomalies affecting splanchnic bed monitoring (such as congenital heart disease, abdominal wall defects, or congenital diaphragmatic hernia), inherited metabolic disorders, hydrops fetalis, TORCH infections, multiple organ failure, spontaneous intestinal perforation, lesions in the area where the NIRS sensor was placed, or

whose UVC was removed for any reason before 24 hours, as well as those with severe anemia or polycythemia, were excluded from the study. Infants with a birth hemoglobin (Hb) level of 10 g/dl or below were considered severely anemic, and those with a Hb level of 22 g/dl or above were considered polycythemic.

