Infants with an UVC were included in the UVC (+) Study Group, while those without a catheter were included in the UVC (-) Control Group. Continuous measurements taken during the first WOL were compared both between the groups and within each group on a day-to-day basis. Splanchnic NIRS monitoring was terminated 24 hours after the removal of the UVC. In the UVC (+) Group, the day and time of catheter placement and removal were recorded. Splanchnic oxygenation measurements were compared at the following time intervals: one hour before UVC placement, one hour after UVC placement, 24 hours before UVC removal, and 24 hours after UVC removal. Additionally, the daily means in the UVC (+) Group during the period when the UVC was in place were compared with the daily means in the UVC (-) Group. Clinical parameters and splanchnic NIRS data were compared between the UVC (+) and UVC (-) Groups. The birth hemoglobin (Hb) value of the UVC (+) Group, as well as the Hb value on the day the UVC was removed, were recorded, and a repeated measures analysis was performed.

The primary outcomes included comparing continuously recorded  $\text{rSO}_2\text{S}$  and  $\text{FOE}$  values during the first WOL between the UVC (+) and UVC (-) groups, assessing  $\text{rSO}_2\text{S}$  and  $\text{FOE}$  measurements within the UVC (+) Group before and after UVC placement and removal, and determining the impact of UVC on splanchnic oxygenation. The secondary outcomes involve evaluating the relationship between UVC presence and the incidence of feeding intolerance and necrotizing enterocolitis.

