### **1.5.2. Statistical analysis**

The statistical data were analyzed using IBM SPSS 21.0 software (IBM Corp. Released 2012. IBM SPSS Statistics for Windows, Version 21.0. Armonk, NY: IBM Corp.). The normality of variable distribution was assessed by Shapiro-Wilk test. The data were presented as a mean±standard deviation (SD), median (Q1–Q3), frequency, and percentage. For comparing normally distributed groups with two groups, the independent samples t-test was used. For comparing non-normally distributed groups with two groups, the Mann-Whitney U test was used. For comparing values at different time points, the Wilcoxon test was used when there were two groups, and the Friedman test was used when there were three or more groups. For repeated measurements, the two-way repeated measures ANOVA (One Factor Repetition) test was used. To determine the direction and magnitude of the relationship (correlation) between variables, Pearson correlation coefficients were calculated for normally distributed variables, and Spearman correlation coefficients were calculated for non-normally distributed variables. For the analysis of cross-tabulations, Pearson Chi-Square, Yates' Chi-Square, and Pearson Exact Chi-Square tests were used. The McNemar-Bowker test was used for comparing categorical clinical findings at two different time points. Covariance analysis was used to assess the importance of the model that had been installed with the confounding factors. A p-value of <0.05 was considered the criterion for statistical significance.

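### Several primary comparisons are each judged at p<0.05 with no lead test, order or multiplicity rule; if any one positive counts, familywise error is about 10–18.5% for four tests

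*Combined protocol and SAP*

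**What the plan says.** The outcomes paragraph at the end of section 2.5 begins "The primary outcomes included comparing continuously recorded" rSO2S and FOE values in the two groups over the first week of life. The same sentence adds rSO2S and FOE "measurements within the UVC (+) Group before and after UVC placement and removal", and then a general aim about the effect of the UVC that has no test attached.

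Earlier in section 2.5 the within-group windows are listed: "Splanchnic oxygenation measurements were compared at the following time intervals: one hour before UVC placement, one hour after UVC placement", followed by the 24 hours before and the 24 hours after removal. A separate sentence there says "Continuous measurements taken during the first WOL were compared both between the groups and within each group on a day-to-day basis".

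Section 1.5.2 assigns tests by data type, not by outcome. For time points, "the Wilcoxon test was used when there were two groups, and the Friedman test was used when there were three or more groups". It also says "For repeated measurements, the two-way repeated measures ANOVA (One Factor Repetition) test was used", without tying that test to the primary outcome. One criterion, p<0.05, covers everything.

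Section 1.5.1 asks for at least 21 infants per group for UVC (+) versus UVC (-), with Type-1 error 0.05, effect size 0.8 and 80% power. It does not say which measure this serves, or whether the test is one- or two-sided.

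**The concern.** The sample size treats the study as one comparison at 5%, but the outcomes sentence describes several of equal standing. No text says which decides the study, in what order they are read, how alpha is shared, or how many must be positive. Each test alone keeps its 5%; the set does not, if one positive result is enough.

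The practical cost is in interpretation. A reader shown one significant result, for example FOE around catheter removal, cannot tell whether it is the planned primary answer or one of several chances to find something.

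**Working it through.** **1. The plan's own figure.** Inputs from section 1.5.1: d = 0.8, alpha 0.05, power 80%, equal groups. For a two-sample t-test (noncentral t), one-sided 0.05 needs 20.03, rounded up to 21 per group, which matches the plan. Two-sided 0.05 needs 25.52, rounded up to 26. At 21 per group, power is 0.817 one-sided and 0.716 two-sided. The calculation is for a single test on either reading.

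**2. Counting primary tests** (sections 2.5 and 1.5.2).
- Four: 2 measures × (one between-group test + one Friedman test over the four windows).
- Six: 2 measures × (between-group + placement + removal), the last two by Wilcoxon.
- Eighteen: 2 measures × 7 daily between-group tests = 14, plus 4 Wilcoxon tests. This requires reading the day-to-day sentence as part of the primary outcome.

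**3. Formula.** Assume that every null is true, each test is at 0.05, any one positive counts as success, and the contrasts (between-group, placement, removal) are independent of each other. Within a contrast, the rSO2S and FOE test statistics have absolute correlation ρ.

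- Per pair: p₂(ρ) = 1 − P(|Z₁| ≤ 1.96 and |Z₂| ≤ 1.96), bivariate normal.
- Familywise error = 1 − (1 − p₂)^m, with m = 2 pairs (four tests) or m = 3 pairs (six tests).

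| ρ (assumed) | p₂ | 4 tests | 6 tests |
|---|---|---|---|
| 0 | 0.0975 | 18.5% | 26.5% |
| 0.7 | 0.0834 | 16.0% | 23.0% |
| 0.9 | 0.0704 | 13.6% | 19.7% |
| 0.95 | 0.0646 | 12.5% | 18.2% |
| 0.99 | 0.0566 | 11.0% | 16.0% |
| 1 | 0.0500 | 9.75% | 14.3% |

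Example for ρ = 0.95: 1 − (1 − 0.0646)² = 0.125. A null simulation with actual t-tests and Friedman tests at 21 per group (day correlation 0.7, 4,000 runs) gave 15.0%, 13.1% and 11.3% for four tests at correlations −0.8, −0.95 and −0.99, in line with this approximation.

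**4. Where in the range.** Section 2.5 calculates FOE from SaO2 and rSO2S, and SaO2 has a 90–95% target band during oxygen therapy. The documents give no means or SDs. Assuming rSO2S mean 50–70 and SD 5–15, and SaO2 mean 94 and SD 1.5–3, FOE simulated from (SaO2 − rSO2S)/SaO2 has correlation −0.90 to about −0.999 with rSO2S. That gives about 10–13.6% for four tests and about 15–20% for six.

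**5. Correlated contrasts.** If the contrasts are themselves positively correlated, the figures fall somewhat. At ρ = 0.9 with correlation 0.5 between contrasts, four tests give 12.6% and six give 17.3%.

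**6. Cost of a plain alpha split.** With 21 per group and d = 0.8, two-sided power is 0.497 at 0.05/4 and 0.437 at 0.05/6. Keeping 80% power at 0.05/4 would need 36.4, so 37 per group.

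**The case against.** This is a single-centre observational cohort. Group difference, effect of placement and effect of removal can be seen as separate questions, each reported on its own terms, and familywise control across separate questions is partly a matter of preference. The plan never says that one significant result makes the study positive, and if all had to be positive there would be no inflation. This stands as a limit on the figures: they are conditional on an any-one-positive rule. It does not remove the gap, because the plan declares primary outcomes and a Type-1 error rate of 0.05 without saying which test that rate protects. An all-must-be-positive rule would also have to be written down and powered.

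The repeated-measures ANOVA in section 1.5.2 could supply a single between-group test over the week. That is a fair reading and is why the count can be as low as four. It would still be run for both measures, beside the within-group contrasts.

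A reader might infer that the daily comparisons are primary too. With 18 tests, assuming rSO2S–FOE correlation 0.7–0.9 and between-day correlation 0.5–0.9, familywise error would be about 27–46%. The primary-outcome sentence does not mention daily tests, so the documents do not establish that figure. A reader might also treat some value well above 10% as a floor for four tests. It is not one, because FOE is derived from rSO2S and the two may be almost interchangeable.

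Finally, 0.72 power might be read as proof that the sample size is wrong. Sidedness is not stated and 21 is a minimum, so that does not follow.

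**Conclusion.** The point holds. Several primary comparisons are each judged at p<0.05 with no lead test, order or multiplicity rule, while the sample size covers one group comparison at 0.05. Familywise error is about 10–18.5% for four tests and about 14–26.5% for six, roughly two to five times the nominal level, with the lower part of each range more likely. It is higher only if the daily comparisons are also taken as primary. These sizes rest on three things that the documents do not give: that any one positive result counts, the rSO2S–FOE correlation, and near-independence of the contrasts. Even if FOE duplicated rSO2S exactly, two independent contrasts would give 1 − 0.95² = 9.75%. It should be corrected, but it does not invalidate any single test.

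**What to change.** Name one lead test: the UVC (+) versus UVC (-) effect on rSO2S over the first week, at a stated two-sided 0.05. This is the contrast that the outcomes sentence lists first and the group comparison that the sample size addresses. Take it from one repeated-measures or mixed model with group, day and infant, using all available days. Adjust for prespecified baseline confounders already recorded, at least gestational age and birth weight, in line with the covariance analysis in section 1.5.2. Adjustment matters because the groups are formed by UVC indication and matched only on those two variables; error control alone does not address confounding.

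Test FOE next, only if rSO2S is significant. Report the daily, catheter-in-place, placement and removal contrasts as secondary, either Holm-adjusted or as estimates with confidence intervals.

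Keep day in the model. Section 2.5 says "Splanchnic NIRS monitoring was terminated 24 hours after the removal of the UVC", and section 1.2 excludes only infants "whose UVC was removed for any reason before 24 hours", so included UVC (+) infants may lack late days. In a null simulation assuming removal on days 2–7 and a common drift of 0.15 SD per day, a plain mean of available days gave false-positive rates of 6.7–8.3%; the random-intercept model with group and day stayed at 4.6–5.2%.

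Cost: SAP wording and one model on data already collected. Isolated daily or within-group results below 0.05 can no longer be primary findings. An unadjusted two-sided t-test at d = 0.8 with the minimum 21 per group has about 0.72 power. If the data have been seen, the choice must be labelled post hoc, because it cannot restore prespecified control.

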## **1.5. Data analysis**

### **1.5.1. Sample size**

A power analysis was performed prior to the study using the summary values from our previous study, 'The Effect of Drip Versus Intermittent Feeding On Splanchnic Oxygenation In Preterm Infants With Intrauterine Growth Restriction: A Prospective Randomized Trial' (6). A sample size of at least 21 infants per group (UVC (+) versus UVC (-) group) was estimated to obtain statistically significant results with a Type-1 error rate of 0.05 (95% confidence level), an effect size of 0.8 (high), and 80% power.

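### The 21 per group matches a one-sided calculation; the two-sided t-test implied by the undirected aim has about 72% power at d = 0.8, not 80%

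*Combined protocol and SAP*

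**What the plan says.** Section 1.5.1 (Sample size) gives the result as "A sample size of at least 21 infants per group (UVC (+) versus UVC (-) group) was estimated to obtain statistically significant results", at a Type-1 error of 0.05, with "an effect size of 0.8 (high), and 80% power". It refers to summary values from the group's previous feeding trial. It does not name the test, its sidedness, the outcome (rSO2S or FOE) or the effect-size metric.

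Section 1.5.2 (Statistical analysis) lists the candidate methods. For two groups: "For comparing normally distributed groups with two groups, the independent samples t-test was used", with Mann-Whitney U when the data are not normal. For serial data: "For repeated measurements, the two-way repeated measures ANOVA (One Factor Repetition) test was used". Covariance analysis is listed for confounders. The only decision rule is "A p-value of <0.05 was considered the criterion for statistical significance", again without sidedness.

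The primary outcomes, in section 2.5 (Data collection), include comparing rSO2S and FOE between the groups over the first week and "determining the impact of UVC on splanchnic oxygenation". No direction is given. The same section adds: "Continuous measurements taken during the first WOL were compared both between the groups and within each group on a day-to-day basis".

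**The concern.** The four stated quantities (21 per group, effect size 0.8, alpha 0.05, 80% power) fit together for a two-group t-test only if the test is one-sided. Nothing else in the plan points to a one-sided test. The aim is to find the effect of the catheter in either direction, and one p<0.05 rule covers a set of tests that are non-directional as normally run.

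A reader therefore cannot tell which comparison has 80% power. If the group comparison is a two-sided t-test on 21 per group, the chance of missing a true difference of d = 0.8 is about 28%, not 20%. Absence of a significant difference in rSO2S or FOE would then be read as stronger evidence of no catheter effect than the design supports.

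**Working it through.** **Inputs.** From section 1.5.1: n = 21 per group, equal groups, alpha = 0.05, effect size 0.8, power 80%. Assumption: 0.8 is Cohen's d; the metric is not named, but the label *high* fits it. The tests come from section 1.5.2. Sidedness is not stated, so both versions are computed.

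**Method.** Two independent samples, noncentral t with 2n − 2 degrees of freedom and noncentrality d·√(n/2). At n = 21 the noncentrality is 0.8 × √10.5 = 2.592 on 40 df. The critical value is 1.684 one-sided and 2.021 two-sided.

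**Reproducing the plan's figure, and the two-sided counterpart.**

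| t-test, d = 0.8, alpha 0.05 | n for 80% | Power at 20 | Power at 21 | Power at 26 |
|---|---|---|---|---|
| One-sided | 20.03 → 21 | 79.9% | 81.7% | 88.5% |
| Two-sided | 25.52 → 26 | 69.3% | 71.6% | 80.7% |

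So 21 is exactly the one-sided minimum, and the two-sided requirement is five more per group. With 21 per group, a two-sided t-test reaches 80% power only at d = 0.886, or at d = 0.8 with alpha raised to 0.089.

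**Mann-Whitney U (normal data).** Dividing the t-test n by the asymptotic relative efficiency 3/π = 0.955:
- One-sided: 20.03 / 0.955 = 20.98 → 21. Simulated power at 21 is 79.6%, so this match is borderline.
- Two-sided: 25.52 / 0.955 = 26.7 → 27. Power at 21 is about 69.5% from the efficiency and 69.3% by simulation.

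**Could a two-sided repeated-measures group effect give 80% at 21?** With m daily means, a constant daily difference and equal within-infant correlation ρ, the effective effect is 0.8 / √[(1 + (m − 1)ρ)/m]. For m = 7 and ρ = 0.5 this is 0.8 / √(4/7) = 1.058.

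| Assumed ρ, m = 7 | Two-sided power at 21 per group |
|---|---|
| 0.5 | 91.7% |
| 0.7 | 83.5% |
| 0.8 | 79.4% |
| 0.9 | 75.3% |

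The highest ρ that still gives 80% is 0.78 for 7 days, 0.77 for 5, 0.72 for 3 and 0.63 for 2. The plan gives no value for ρ.

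**Covariance analysis.** The effective effect is 0.8 / √(1 − r²) on 39 df. Two-sided power of 80% at 21 per group needs a covariate–outcome correlation r of about 0.43. The plan gives no value for r.

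**The case against.** The strongest reply is that no figure in section 1.5.1 is shown to be impossible. The 21 is the correct one-sided answer, and two-sidedness is inferred, because an undirected aim does not reveal which option was used in the power calculation. This stands, and it is why the conclusion is conditional. It does not remove the problem: a one-sided basis is neither stated nor consistent with the aim and the significance rule.

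Second, the powered analysis may have been the repeated-measures ANOVA, since the primary outcome covers the whole first week. Some two-sided designs of that kind give 21; for example, 7 days with ρ = 0.75 needs 20.28 per group. This also stands as a possibility, but it needs a correlation the plan does not report. The gain does not carry over to a t-test between groups on a single day, and day-by-day comparisons are planned. Covariate adjustment could help on a single day too, again only with an unstated correlation.

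Third, 21 is a minimum, the study has already been conducted, and the remedy is wording. All true. If 26 or more per group were enrolled, the t-test shortfall disappears; the documents do not give the enrolled number.

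**Conclusion.** The concern holds. For the two-group t-test, 21 per group delivers 80% power at d = 0.8 only if the test is one-sided. Read as two-sided, power is 71.6%, a shortfall of 8.4 percentage points, and 80% needs 26 per group.

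This rests on three assumptions: 0.8 is Cohen's d, the powered comparison is a single unadjusted two-group t-test, and the test is two-sided. The arithmetic is certain given these. The third is an inference from the wording of the aim and the significance rule. The point is one to correct: it changes no estimate or test, but it does change how a null group comparison should be read.

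**What to change.** In section 1.5.1, name the test, its sidedness, the outcome to which the effect size applies (rSO2S or FOE) and the effect-size metric. Then:

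- If the basis is the two-sided t-test, state that 21 per group gives about 72% power for d = 0.8, or 80% power for d = 0.89, at alpha 0.05. If 26 or more per group were enrolled, add that this number gives 80% for d = 0.8.
- If the basis was one-sided, say so, give the direction and its justification, and align section 1.5.2.
- If it was repeated-measures or covariate-adjusted, give the number of days and the assumed correlation, and identify that analysis in section 1.5.2 as the one that was powered.

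The cost is wording only, with no extra enrolment. On the two-sided t-test reading, the reported power becomes less favourable.

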### **1.5.2. Statistical analysis**

The statistical data were analyzed using IBM SPSS 21.0 software (IBM Corp. Released 2012. IBM SPSS Statistics for Windows, Version 21.0. Armonk, NY: IBM Corp.). The normality of variable distribution was assessed by Shapiro-Wilk test. The data were presented as a mean±standard deviation (SD), median (Q1–Q3), frequency, and percentage. For comparing normally distributed groups with two groups, the independent samples t-test was used. For comparing non-normally distributed groups with two groups, the Mann-Whitney U test was used. For comparing values at different time points, the Wilcoxon test was used when there were two groups, and the Friedman test was used when there were three or more groups. For repeated measurements, the two-way repeated measures ANOVA (One Factor Repetition) test was used. To determine the direction and magnitude of the relationship (correlation) between variables, Pearson correlation coefficients were calculated for normally distributed variables, and Spearman correlation coefficients were calculated for non-normally distributed variables. For the analysis of cross-tabulations, Pearson Chi-Square, Yates' Chi-Square, and Pearson Exact Chi-Square tests were used. The McNemar-Bowker test was used for comparing categorical clinical findings at two different time points. Covariance analysis was used to assess the importance of the model that had been installed with the confounding factors. A p-value of <0.05 was considered the criterion for statistical significance.

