### **1.4.Umbilical Venous Catheter Placement, Use, and Removal**

In our NICU, UVC placement is a sterile bedside procedure carried out by pediatric residents, neonatology fellows, and neonatology specialists, using polyurethane, single-lumen catheters sized according to the infant's weight: 3.5 Fr for those under 1500 g and 5 Fr for those over 1500 g. Catheter placement is performed using the Modified Shukla-Ferrara Formula. The position of the catheters is confirmed with chest and/or abdominal radiographs before they are secured. Fluids and medications administered through the catheter are prepared under sterile conditions, and unfractionated heparin at a concentration of 0.5 IU/ml is added to intravenous

fluids and parenteral nutrition solutions. The recommended maximum duration of catheter use in our unit is 7-10 days for UVC.

During follow-up, any catheter malposition, and the postnatal day on which it occurred, if applicable, were recorded. Malposition was defined as follows: The optimal placement of the UVC is at the junction of the inferior vena cava and the right atrium. This area corresponds to the T9-10 level on an anteroposterior chest film (8). In preterm infants, even a difference of one vertebral level on a direct radiograph can be significant. Therefore, in addition to thoracic vertebral levels, the level of the right hemidiaphragm can also be used as a reference point for the catheter tip on direct radiographs. Catheters positioned further intracardially or at a lower level are considered malpositioned (9).

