Postnatal morbidities such as respiratory distress syndrome (RDS), hemodynamic significant patent ductus arteriosus (HsPDA), grade 2-3 intraventricular hemorrhage (IVH), FI, NEC, and sepsis were noted. Gastric residual volume of more than 50% of the previous feeding volume, emesis, abdominal distention, or both, and a reduction, delay, or cessation of enteral feedings were the criteria used to define feeding intolerance (8). According to the modified Bell's criteria (9), stage II/III NEC was used as an outcome parameter. Echocardiography was used to determine the presence of HsPDA. Positive blood culture was used to define proven sepsis. The Papile classification system was used to classify IVH (10). Furthermore, the need for inotropic support during the first week of life, parenteral nutrition durations, invasive/non-invasive mechanical ventilation support, total respiratory support, oxygen support, hospitalization, and mortality were recorded.

**(b) Splanchnic near-infrared spectroscopy (NIRS) monitoring:** As soon as the infants were admitted to the NICU on the first day of life (DOL), a self-adhesive transducer (cerebral/somatic-neonatal NIRSensor) with a light-emitting diode and two remote sensors was applied to the infra-umbilical abdominal region to continuously record regional splanchnic saturation (rSO2S). Continuous rSO2S monitoring was carried out for 1 week using NIRS (INVOS 5100; Covidien Somanetics, Troy, MI), simultaneously together with continuous preductal oxygen arterial saturation (SaO2) monitoring using a pulse oximetry device (Nellcor, Covidien-Medtronic, Minneapolis, MN) with a target band of 90–95% and alarm settings of 89 and 96% in the case of oxygen therapy. Based on the simultaneous measurements of rSO2S and

$\text{SaO}_2$ , the infants' fractional tissue oxygen extractions ( $\text{FOE} = \text{SaO}_2 - \text{rSO}_2\text{S} / \text{SaO}_2$ ), which represent the balance between oxygen delivery and oxygen consumption, were assessed. After removing artifacts that may indicate sensor misplacement,  $\text{SaO}_2$  and NIRS parameters ( $\text{rSO}_2\text{S}$ ,  $\text{FOE}$ ) were calculated as means on each day of the first week of life (WOL).

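### The repeated-measures ANOVA that best fits the first-week comparison keeps only infants with a mean on every day, and the plan has no rule for missing days

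*Combined protocol and SAP*

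**What the plan says.** Section 2.5(b) reduces continuous recordings to one mean per infant per day of the first week, "After removing artifacts that may indicate sensor misplacement". It compares these values between and within the groups day by day. It also compares UVC (+) daily means, restricted to the days with the catheter in place, with those of the controls. The first-week rSO2S and FOE comparison is among the primary outcomes.

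For the analysis, section 1.5.2 says "For repeated measurements, the two-way repeated measures ANOVA (One Factor Repetition) test was used" and "The statistical data were analyzed using IBM SPSS 21.0 software". It also lists t-tests and Mann-Whitney tests for two groups, and the Friedman test for three or more time points.

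On the length of recording, section 2.5(b) first says that "monitoring was carried out for 1 week using NIRS" and later that "Splanchnic NIRS monitoring was terminated 24 hours after the removal of the UVC". Section 1.2 excludes infants "whose UVC was removed for any reason before 24 hours", so any later removal is eligible. Section 1.4 adds: "The recommended maximum duration of catheter use in our unit is 7-10 days for UVC". No distribution of catheter duration is given.

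The plan has no rule for a missing daily mean, no minimum recording time per day, and no allowance in the sample size for incomplete infants.

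**The concern.** A classical repeated-measures ANOVA works on one complete row per infant. An infant without a mean on one of the days analysed is removed from the test, including the days that were recorded. The Friedman test within a group behaves in the same way.

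If recording stopped 24 hours after removal, the loss depends on catheter duration and can arise only in the UVC (+) group. The infants kept would be those who needed the catheter longer, compared with controls who face no such filter. Controls were matched on gestational age and birth weight, and dropping part of one group by catheter duration weakens the balance that matching was meant to give. So comparability is at stake as well as precision.

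The comparison limited to in-place days is uneven by construction, because each infant's series ends at removal. The plan names no test for it.

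**Working it through.** **1. The plan's own figure.** Section 1.5.1 gives 21 per group for an effect size of 0.8, alpha 0.05 and 80% power. Sidedness is not stated. For a two-sample t-test with n1 and n2 infants, the noncentrality is 0.8 × √(n1·n2/(n1+n2)) on n1+n2−2 degrees of freedom. With 21 and 21 this is 0.8 × √(441/42) = 2.59 on 40. A one-sided test needs 21 per group (power 82%), which matches the plan. A two-sided test needs 26, and 21 per group gives 72%. Sidedness is a separate matter. Two-sided power is used below, with 72% as the reference.

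**2. If recording ended 24 hours after removal.** Removal on day r gives data to day r+1, so a day-7 mean exists only if r is 6 or later. The removal distributions are assumptions:

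| Removal uniform on days | Share complete | UVC (+) complete of 21 |
|---|---|---|
| 2-8 | 3/7 | 9 |
| 2-10 | 5/9 | 11.7, about 12 |
| 7-10 | 4/4 | 21 |

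**3. If recording ran the full week.** Only a day with no usable mean removes an infant. With an assumed chance p of losing a whole day, independent across days, the share complete is (1−p)^7:

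| p | (1−p)^7 | Complete of 21 | Two-sided power, both groups reduced |
|---|---|---|---|
| 2% | 0.868 | 18.2, about 18 | 65% |
| 5% | 0.698 | 14.7, about 15 | 56% |
| 10% | 0.478 | 10.0, about 10 | 40% |

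**4. Both sources together.** Assume 2% daily loss in both groups and a share of UVC (+) infants who stop before day 7.
- 25% stopping early: 21 × 0.75 × 0.868 = 13.7, about 14, against 18. Noncentrality is 0.8 × √(252/32) = 2.24 on 30 degrees of freedom; power 58%.
- 50% stopping early: 21 × 0.50 × 0.868 = 9.1, about 9, against 18. Noncentrality is 0.8 × √(162/27) = 1.96 on 25 degrees of freedom; power 47%.

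**5. Using all available days.** Step 4 was simulated with 4,000 runs per setting, within-infant correlation 0.5 or 0.8, and early stopping unrelated to outcome. An analysis weighting each infant by the days available kept about 70-71% power in both cases. Analysing complete infants only gave about 58% and 47%. The simulation speaks to precision. It does not test bias from removal that is related to the infant's condition.

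**The case against.** The strongest reply is that the plan never assigns this ANOVA to the daily means. Section 2.5 speaks of a repeated measures analysis only for hemoglobin, and a day-by-day comparison could mean a t-test or Mann-Whitney test on each day. Those tests keep an infant on every day with data. This stands as a limit: the loss belongs to the ANOVA and to Friedman, not to every listed analysis. The inference remains strong, because the hemoglobin data have two time points in one group and do not fit a two-way design, whereas group by day does.

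The second reply is that the catheter-dependent loss rests on one side of an unresolved conflict. If recording lasted a week for everyone, that loss and its selection effect disappear from the seven-day comparison. This also stands, and it is why the size cannot be fixed from the documents.

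A reader might infer that any artifact removes an infant. The documents do not support that: artifact is deleted from continuous recordings before averaging, and a partly affected day still yields a mean. A reader might also infer that the controls are unselected or suffer no loss. They are matched, and they can lose whole days like anyone else.

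**Conclusion.** The point holds in a conditional form. If the two-way ANOVA is used for first-week rSO2S and FOE, infants without every daily mean are dropped, and nothing in the plan prevents or discloses it. Whether the loss also selects UVC (+) infants by catheter duration depends on which statement in section 2.5 describes the actual recording.

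A reader might conclude that fewer than half of the UVC (+) infants enter the primary analysis. The documents do not support that as a finding. The figure of 9 of 21 comes from one assumed removal distribution, and other assumptions compatible with section 1.4 give about 12 or all 21. The whole-day loss rates of 2%, 5% and 10% are likewise assumptions and treat days as independent. What is firm is the mechanism and the absence of a missing-day rule. The method should be changed because a better one is available at little cost.

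**What to change.** Reconcile the two statements in section 2.5 on when recording ended, for both groups. In section 1.5.2, name the test used for first-week rSO2S and FOE, and replace the two-way repeated-measures ANOVA there with a linear mixed model. The model should contain group, day and group-by-day, with a parsimonious covariance stated in advance, such as compound symmetry or AR(1), and should use every available daily mean. Use the same model for the comparison restricted to in-place days. Report the number of infants contributing on each day in each group, and state how much usable recording makes a daily mean.

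The cost is small: no new data, and the MIXED procedure is in the same software. Because the text describes recruitment ending in February 2024, it may mean rerunning a completed analysis as well as changing the wording. There are two real downsides. A covariance structure must be chosen: an unstructured one over seven days has 7 × 8/2 = 28 parameters, too many for about 42 infants. The model also assumes that days are missing at random, so bias can remain if removal follows clinical condition that the model does not include.
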